### **Aim 1: To determine the effects of aerobic exercise paired with UE repetitive task practice compared to time-matched UE task practice on the recovery of UE motor function in individuals with stroke.**

**Rationale:** Declines in UE function are common in the majority of patients with stroke. Aerobic exercise has been theorized to facilitate motor recovery following stroke; however, the proposed study will be the first to test this to theory empirically. Our preliminary data indicate that our AE approach combined with a reduced dosage of RTP resulted in significantly greater gains in motor function than time-matched RTP without an AE component, supporting the scientific hypothesis that AE facilitated motor recovery associated with RTP.

**Outcomes:** The primary clinical outcomes to evaluate changes in motor function and impairment are the Action Research Arm Test (ARAT) and Fugl-Meyer Assessment (FMA), respectively. To determine the impact on motor control processes, participants will complete a bimanual dexterity task in which grasping forces and torques will be quantified. Finally, the Wolf Motor Function Test (WMFT) will serve as a secondary outcome.

**Expected results and interpretation:** It is hypothesized that the AE+RTP group will demonstrate greater improvements in UE motor function and impairment compared to RTP only. Animal and human studies suggest that intensive AE facilitates neurophysiologic changes in the brain, several of which have been implicated neuroplasticity. Preliminary data from our R03 study demonstrated improved motor outcomes in those completing AE+RTP compared to RTP only, implying that AE may exploit the motor learning benefits associated with RTP and could be used to decrease the dosage of RTP required for UE motor recovery.

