### **Data analysis**

**Consideration of Relevant Biological and Sociological Variables:** Participants in both groups will be compared on potentially confounding baseline variables (age, gender, socio-economic status, education, fitness, co-morbidities, degree of hemiplegia, location/type of stroke, side of lesion) to assess the extent of any imbalances across groups. Baseline variables in which there is a clinically important difference between groups may be included as covariates. Participants will also be compared using participation and adherence metrics. While recent evidence has shown that genetic polymorphisms may influence motor recovery following stroke, it is beyond the scope of this project due to cost and lack of expertise to consider these as covariates.

**Analysis of Motor Outcomes (Aim 1):** Motor outcomes for each group will be compared at baseline, mid-treatment, EOT, and EOT+4. The group effect on ARAT, FMA, and WMFT will be estimated using separate linear mixed effects models with a random effect for subject, fixed effects for group, examination time, and baseline value of the outcome. An appropriate covariance structure (e.g.: unstructured, compound symmetric, autoregressive) will be used as determined using Akaike's information criterion. The effects of group, time, and the group-by-time interaction will be assessed for each outcome. To adjust for multiple comparisons, the family-wise error rate will be controlled via Bonferroni-type adjustment required for multiple comparisons. Tukey's and other post-hoc comparisons will be used to explore pairwise differences in main effects of group membership. To further investigate the effect of the intervention group assignment on the various sub-scales of the ARAT, a multivariate analysis of variance will be used along with a separate principle component analysis to study if further dimension reduction is possible in using these two tests in the study. Transformations of the data will be made to achieve normality or other model assumptions. The overall alpha level will be set at 0.05.

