### **Power and Sample Size Justification:**

The power and sample size calculation is based on FMA scores from our R03 study. A minimal clinically important difference (MCID) range of 4.25-7.25 points has been reported for the FMA with baseline subject standard deviation of 5.7 – 6.3 points. To be conservative, we have assumed the MCID to be 4.25 for the purposes of our power calculations. Based on results from our R03 which included 3 intervention groups, the forced AE+RTP group, voluntary AE+RTP group, and RTP only groups improved on the FMA by a mean of 12.33(4.13), 4.83(4.91), and 4.4(4.87), respectively. In the sample size and power computation, it is assumed that there is an increase of 2\*MCID for the AE+RTP group and 1\*MCID for the RTP only group, along with

statistically significant differences between the groups at EOT. Further, it is assumed that subject SD will remain ~10 points within the group. Based on these assumptions, with n=30 in each of the intervention groups, we will have a .87 power at the 0.05 significance level to detect pairwise group differences equivalent to an effect size of .4. All computations were completed using the PASS 13 program (East Kaysville, Utah).

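### The .87 power covers FMA alone at an unadjusted 0.05, does not follow from its own stated inputs, and leaves ARAT, the one outcome labelled primary throughout, with no power figure

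*Combined protocol and SAP*

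**What the plan says.** - **Primary outcomes.** Aim 1, Outcomes: "The primary clinical outcomes to evaluate changes in motor function and impairment are the Action Research Arm Test (ARAT", and the same sentence adds the FMA; WMFT is secondary. The hypothesis there is that "the AE+RTP group will demonstrate greater improvements in UE motor function and impairment compared to RTP only". The Data Variables section tags ARAT as primary and WMFT as secondary, and gives FMA no tag.
- **Tests and error control.** Data analysis, Aim 1 paragraph: ARAT, FMA and WMFT each get their own mixed model. "The effects of group, time, and the group-by-time interaction will be assessed for each outcome". The next sentence says that "the family-wise error rate will be controlled via Bonferroni-type adjustment required for multiple comparisons", and the paragraph ends "The overall alpha level will be set at 0.05". It does not say which tests form the family, what alpha each receives, or whether success needs one primary or both.
- **Power.** Power and Sample Size Justification: "The power and sample size calculation is based on FMA scores from our R03 study". The MCID is taken as 4.25 points, with a gain of twice that in AE+RTP and once that in RTP only, and differences are considered at end of treatment (EOT). Then "it is assumed that subject SD will remain ~10 points within the group", and with 30 per group "we will have a .87 power at the 0.05 significance level to detect pairwise group differences", for an effect size given as .4. The type of effect size and the sidedness are not stated. No ARAT difference, SD or power appears.

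**The concern.** The power figure and the analysis it should support do not describe the same test. The analysis promises an overall 0.05 across multiple comparisons; the power is computed at 0.05 for one outcome. If FMA shares alpha with ARAT, it is tested at a stricter level than the one used for power. If ARAT is the sole primary, as the Data Variables section can be read, the trial's only power figure belongs to an outcome without that label.

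The .87 also looks inconsistent with the difference and SD printed beside it, so it is not a safe starting point for any adjusted figure. At stake is whether a reader can rely on the stated power, and how a split result (one of ARAT and FMA significant, the other not) would be interpreted.

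**Working it through.** **Inputs from the power section.** n = 30 per group; difference 2 × 4.25 − 1 × 4.25 = 4.25 points; SD about 10; effect size .4; alpha 0.05; stated power .87. Two-sided testing is assumed.

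**Formula.** Two-sample t test with 58 degrees of freedom and noncentrality d × √(30/2). The critical value is 2.002 at 0.05 and 2.301 at 0.025. Power is the noncentral-t probability beyond ± the critical value.

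**Step 1: reproduce .87.** The section's own difference and SD give d = 4.25/10 = 0.425, noncentrality 0.425 × 3.873 = 1.646, and power 0.367. Taking .4 as d gives 0.332. One-sided, these become 0.493 and 0.455. None is near .87. If .4 is Cohen's f, then d = 2 × 0.4 = 0.8 for two equal groups, the noncentrality is 3.098, and power is 0.861 (0.8725 by normal approximation). That reproduces .87 closely, but d = 0.8 is not 4.25/10.

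An exact .87 needs d = 0.810, that is an SD of 4.25/0.810 ≈ 5.24. Starting from SD 10, baseline adjustment reaches this only with a baseline-to-EOT correlation of about 0.85, since 10 × √(1 − 0.85²) = 5.27 gives power 0.867. The plan states no such correlation.

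**Step 2: FMA power if ARAT and FMA share 0.05 by Bonferroni (0.05/2 = 0.025 each).**

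| FMA input | d | at 0.05 | at 0.025 |
|---|---|---|---|
| .4 read as f | 0.800 | 0.861 | 0.785 |
| 4.25 / 5.7 (lower baseline SD quoted) | 0.746 | 0.811 | 0.720 |
| 4.25 / 6.3 (upper baseline SD quoted) | 0.675 | 0.729 | 0.624 |
| 4.25 / 10 (the plan's assumption) | 0.425 | 0.367 | 0.264 |
| 4.25 / 4.91 (largest R03 change SD) | 0.866 | 0.909 | 0.850 |
| 4.25 / 4.13 (smallest R03 change SD) | 1.029 | 0.975 | 0.951 |

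The adjustment costs about 8 to 11 points of FMA power in the first four rows and 2 to 6 points in the last two. The drop from .87 to 0.367 is a separate matter that multiplicity does not cause.

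**Step 3: power of a claim that involves both outcomes.** ARAT inputs are absent, so equal effects and a correlation of 0 to 0.9 between ARAT and FMA are assumed. Simulated t tests at d = 0.8 on both give:
- at least one significant at 0.025 each: 0.95 at correlation 0, falling to 0.84 at 0.9;
- both significant at 0.05 each: 0.74 at correlation 0, rising to 0.82 at 0.9.

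At d = 0.425 on both, the chance that both are significant at 0.05 is 0.13 to 0.30.

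**Step 4: error if both were tested at 0.05 and either sufficed.** With independent outcomes it is 1 − 0.95² = 0.0975; at correlation 0.9 it is about 0.07 (simulated). Both exceed the promised overall 0.05.

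**The case against.** Several counter-arguments have force.

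- **The plan already promises error control.** This stands in part. A reader might infer that the trial plans to run at an error of 0.0975. It does not: testing both primaries at 0.05 with either sufficing would contradict the stated overall 0.05. The figure shows only what loose wording would permit, for instance if the adjustment were applied solely within each outcome.
- **Sharing alpha need not weaken the Aim 1 claim.** This stands. A reader might infer that splitting alpha deprives the whole aim of its stated power. At d = 0.8 on both outcomes, the chance of at least one success at 0.025 each is about .87 or more unless the outcomes are highly correlated. The loss holds for FMA taken alone.
- **ARAT may be the sole primary.** The Data Variables section allows this, and the alpha split would then fall away. But the labelled primary would have no power basis, so the gap moves and does not close.
- **The power section says openly that it rests on FMA.** True, and it claims no ARAT or joint power. The figure still has to match the alpha at which FMA will be tested.
- **.87 may have another source.** The R03 forced-exercise and RTP-only gains differ by 12.33 − 4.4 = 7.93; over SD 10 this is d = 0.793, f of about .4, and power 0.855. That is plausible, but it is inference: the section says that it assumes a one-MCID difference. The smaller R03 change SDs would give more than .87, but the section says about 10.

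**Conclusion.** The point holds as a correction to the power statement. The .87 is for FMA alone, at an alpha that takes no account of the promised adjustment, and it cannot be obtained from the stated 4.25 points and SD of about 10, which give 0.367. With alpha shared equally between ARAT and FMA, FMA power is 0.785 if .4 means Cohen's f, and 0.264 on the printed difference and SD. ARAT power cannot be computed from the documents at all.

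These figures rest on two-sided t tests and full follow-up of 30 per group. The two-outcome figures also rest on equal effects and an assumed correlation. The 0.025 split is one possible rule; the plan does not specify it.

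The documents do not support the stronger conclusion that the trial must be enlarged. Which difference and SD apply is for the sponsor to confirm, and some of the quoted SDs give ample power. The missing family and success rule would by themselves be mainly a lack of detail. They matter here because they determine the alpha at which the power must be restated.

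**What to change.** 1. **Power and Sample Size Justification.** Reconcile .87 with the 4.25-point difference, the SD of about 10 and the effect size .4: say whether .4 is d or f, and which SD or baseline adjustment was used. Then restate FMA power at the alpha actually applied. Give ARAT power at that alpha, or say that the trial is not sized for ARAT.
2. **Aim 1 and Data Variables.** Make the two sections agree on whether ARAT alone, or ARAT and FMA, are primary.
3. **Data analysis, if both are primary.** State that the confirmatory family is the between-group comparison on ARAT and FMA, and give the success rule. If either suffices, use Holm at overall 0.05, or 0.025 each. Holm is never less powerful than plain Bonferroni; with d = 0.8 on both, FMA power is about 0.82 to 0.845 over correlations 0.9 to 0. If both are required, test each at 0.05 and report joint power. Naming the deciding time point in the same sentence would help; the power section already refers to EOT.

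The cost is a few sentences and one recalculation. Outcomes, design and sample size stay as they are. The downside is that the stated FMA power will probably look less favourable, by an amount that depends on the inputs the sponsor confirms.

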
### **Approach**

**The proposed project determining the clinical effectiveness of AE in facilitating motor recovery and determining the cost-effective strategy could fundamentally alter current rehabilitation approaches and drive the adoption of AE into stroke rehabilitation.**

**Experimental Overview:** A prospective, single-center, parallel group, rater-blind clinical trial is proposed. A schematic depicting workflow and outcomes is provided in Figure 2. A total of 60 individuals with chronic

stroke (>6 months) will be randomized to one of two time-matched groups: 1) AE and RTP or 2) RTP only. All groups receive an identical dose of contact time (36 hours) over a course of 8 weeks (3X per week). Upper extremity motor outcomes (Aim 1) will be collected at baseline, mid-treatment, end of treatment (EOT), and EOT+4 weeks. Data concerning participant demographics, social determinants, and intervention resource utilization (including personnel) will be collected during the clinical trial and at 6-months (primary outcome on full data set, Aim 2) and 12-months follow-up (secondary outcome on subset of sample, Aim 2).

**The following elements of our experimental design ensure scientific rigor:** 1) Randomization stratified according to baseline function and age; 2) Blinding of the rater; 3) Utilization of a time-matched control group; 4) Sample size justified to demonstrate group differences based on preliminary studies; and 5) Sound statistical analysis plan. An intent-to-treat approach will be used to address any missing data; to date <1% of data in our preliminary studies are missing.

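### The follow-up MANOVA of the ARAT sub-scales names no baseline term, response or visit, although baseline ARAT is collected and the total-score models adjust for it

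*Combined protocol and SAP*

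**What the plan says.** All references are to the combined protocol and SAP.

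- **Total scores (Data analysis, Analysis of Motor Outcomes).** ARAT, FMA and WMFT each get a linear mixed model with a random subject effect and "fixed effects for group, examination time, and baseline value of the outcome".
- **Sub-scales (same paragraph).** As a further look at the group effect, the plan says that "on the various sub-scales of the ARAT, a multivariate analysis of variance will be used along with a separate principle component analysis" follows. It names no covariate, response or visit for this MANOVA.
- **Data available (Approach).** "Upper extremity motor outcomes (Aim 1) will be collected at baseline, mid-treatment, end of treatment (EOT), and EOT+4 weeks".
- **General covariate rule (Data analysis).** "Baseline variables in which there is a clinically important difference between groups may be included as covariates". The variables listed for comparison include degree of hemiplegia but not baseline ARAT.
- **Randomization (Approach).** The design lists "Randomization stratified according to baseline function and age".

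The documents give no SD, correlation or power for the ARAT or its sub-scales.

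**The concern.** The sub-scale analysis is meant to show where in arm and hand function a difference in the ARAT total arises. As written, it does not carry over the adjustment used for the total. If the response is the post-treatment score, the group comparison carries the full between-person spread, and entry is open to FMA scores from 24 to 50. If the response is the change score, the loss is usually smaller but real, and it is larger than on post scores when rho is below 0.5.

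Two things are at stake. The first is precision in an analysis with 30 people per arm. The second is comparability: if sub-scales and total appear to disagree, the reader cannot tell whether treatment or method is the cause. Leaving the response open also allows the choice between post and change scores to be made after the data are seen.

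**Working it through.** **The plan's own figure.** No power or precision is stated for the sub-scale analysis. The only power statement concerns the FMA: "we will have a .87 power at the 0.05 significance level to detect pairwise group differences equivalent to an effect size of .4". Taking 0.4 as Cohen's f (d = 0.8 for two groups), two-sided 0.05 and 30 per arm, the normal approximation gives 0.8 × sqrt(15) = 3.10, and 3.10 − 1.96 = 1.14, so power is 0.87 (0.86 with the t distribution). It reproduces on that reading but says nothing about the sub-scales.

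**Step 1. Formulas.** Take equal SD σ at both visits, n per arm, and correlation rho between a sub-scale's baseline and follow-up scores. The variance of the group difference is:

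- post scores: 2σ²/n
- change scores: 4σ²(1 − rho)/n
- baseline-adjusted: 2σ²(1 − rho²)/n

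The precision lost by not adjusting is therefore rho² on post scores. On change scores it is 1 − (1 + rho)/2 = (1 − rho)/2.

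**Step 2. Range over rho.** The last column is 30/(1 − rho²), the size per arm at which unadjusted post scores would match 30 per arm with adjustment.

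| rho | Lost, post | Lost, change | Post-score n per arm |
|---|---|---|---|
| 0.3 | 9% | 35% | 33 |
| 0.5 | 25% | 25% | 40 |
| 0.7 | 49% | 15% | 59 |
| 0.8 | 64% | 10% | 83 |
| 0.9 | 81% | 5% | 158 |

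**Step 3. Proxy for rho.** The only figures that bear on rho are for the FMA total (Power and Sample Size Justification). The MCID is reported "with baseline subject standard deviation of" 5.7 to 6.3 points, and the pilot changes carry bracketed values of 4.13, 4.91 and 4.87. I read these as SDs. Preliminary Studies gives ±1.6 for the first group, and (4.13/1.6)² = 6.7, about one arm of a 17-person, three-group pilot, which fits 1.6 being the standard error.

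With equal SDs, rho = 1 − SDchange²/(2 × SDbase²):

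- lowest: 1 − 4.91²/(2 × 5.7²) = 1 − 24.11/64.98 = 0.63
- highest: 1 − 4.13²/(2 × 6.3²) = 1 − 17.06/79.38 = 0.79 (0.785 unrounded)

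Loss on post scores: 0.629² = 0.40 to 0.785² = 0.62. Loss on change scores: (1 − 0.785)/2 = 0.11 to (1 − 0.629)/2 = 0.19.

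**Step 4. Sensitivity of the proxy.** The same section assumes an SD of about 10. With SD 10 at both visits, rho is 0.88 to 0.91, and the loss is 77-84% (post) or 4-6% (change). Pairing baseline SD 5.7 with a later SD of 10 and change SD 4.13 gives (32.49 + 100 − 17.06)/(2 × 57) = 1.01, which is impossible. The SD figures do not all fit together, hence the equal-SD cases.

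**Step 5. Power of the multivariate tests.** Simulation with Wilks' lambda, 3,000 runs per setting, 30 per arm and test level 0.05 (the plan: "The overall alpha level will be set at 0.05"). Assumed, not taken from the documents: four sub-scales, between-scale correlation 0.6, and a shift of 0.5 SD on each.

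| rho | MANOVA, post | MANOVA, change | MANCOVA |
|---|---|---|---|
| 0.3 | 0.39 | 0.28 | 0.39 |
| 0.5 | 0.39 | 0.38 | 0.48 |
| 0.7 | 0.39 | 0.62 | 0.66 |
| 0.9 | 0.39 | 0.99 | 0.98 |

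Three or five sub-scales give the same pattern. MANCOVA is best, or within 0.01 of best, in every row. Each unadjusted choice does badly somewhere.

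**The case against.** The strongest reply is that the size of the loss cannot be read from the documents. A reader might infer that half or more of the sub-scale precision will be thrown away. That needs a post-score response and rho of at least about 0.71. The plan states no response, and its language leans towards change: Aim 1 speaks of changes and improvements, and the sample size rests on FMA improvement. On change scores the loss never reaches half for any rho of zero or above. The proxy range itself starts at 0.63, where even post scores lose only 40%. It also comes from another instrument, from a total rather than a sub-scale, and from a small pilot; the baseline SD may belong to the cited MCID source. Single sub-scales may correlate less than a total. All of this stands.

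A reader might also infer that a chance baseline gap will pass unchecked into the sub-scale result. Stratification by baseline function limits that risk, though it does not recover the precision that adjustment would give. The general covariate rule is only a partial answer, because it is optional and depends on an observed imbalance.

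Finally, this is a follow-up analysis with no power claim. That also stands and limits the weight of the point. None of these arguments supplies the missing baseline term, response or visit.

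**Conclusion.** The point holds as a gap and an inconsistency in a follow-up analysis, with a better method available at little cost. How much is lost depends on two things that the plan does not give: the response and the sub-scale correlation. The proxy results in Step 3 are indicative only, since they assume equal SDs and that sub-scales behave like the FMA total.

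The documents do not support a fixed headline loss, nor any claim that the main results are compromised: the ARAT and FMA totals already have baseline in their models. That the sub-scales would actually contradict the ARAT total is a possibility, not something shown here. The case for adjustment does not rest on knowing rho, because in the simulated settings it was never materially worse than either unadjusted analysis.

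**What to change.** Replace the MANOVA with a MANCOVA of the post-treatment ARAT sub-scale scores at one stated visit (for example EOT), with the baseline sub-scale scores as covariates. Report the adjusted group difference for each sub-scale with its confidence interval.

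An alternative is a baseline-adjusted mixed model for each sub-scale with group-by-visit terms. This is not equivalent: the MANCOVA gives one joint test at one visit, whereas separate models give several tests and need stated multiplicity control across sub-scales. The plan should name one of the two in advance.

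The cost is a sentence or two in the Data analysis section and no new data. The covariates use a few degrees of freedom, and if rho is about 0.3 there is almost no gain over post scores (simulated power 0.39 either way).
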